2.1.2 Site/Investigator Eligibility Criteria

To participate in the PETRA trial, investigators and trial sites, i.e. UCL and University of Bristol must fulfil a set of criteria that have been agreed by the Sponsor and PETRA Trial Management Group (TMG) and that are defined below.

Eligibility criteria:

1. A named clinician is willing and appropriate to take Principal Investigator (PI) responsibility
2. Suitably trained staff are available to recruit participants and collect data

Keele University will act as a co-ordinating centre for participants recruited in the North West Coast and the West Midlands region and must fulfil only the second of the eligibility criteria defined above.

2.1.2.1 Principal Investigator's (PI) Qualifications and Agreements

The Principal Investigator(s) must be willing to sign a Principal Investigator Declaration (Schedule 6 of the Clinical Trial Site Agreement), to comply with the trial protocol (confirming their specific roles and responsibilities relating to the trial, and that their site is willing and able to comply with the requirements of the trial). This includes confirmation of appropriate qualifications (provide an up-to-date CV), familiarity with the appropriate use of any investigational products and agreement to comply with the principles of GCP. The PI must agree to permit monitoring and audit as necessary at the site, and to maintain documented evidence of staff who have been delegated significant trial related duties.

2.2 Site approval and activation

Site training will be performed prior to the activation of the UCL and University of Bristol sites and will include all processes for the trial including but not limited to protocol training, data management procedures, procedures for prescribing of investigational medicinal product, adverse event reporting procedures and expectations for monitoring visits. A log of Site Initiation Visit attendees will be kept in the TMF as a record of participants present. The Visit may occur in person or via Videoconference as outlined in the Quality Management and Monitoring Plan (QMMP).

The trial manager or delegate will notify the PI in writing of the plans for site activation. Sites will not be permitted to recruit any participants until a letter for activation has been issued. On receipt of the signed Clinical Trial Site Agreement (including the signed PI Declaration), completed delegation of responsibilities log and staff contact details, the Trial Manager or delegate will complete the green light process and issue written confirmation of site activation to the site PI.

The site must conduct the trial in compliance with the protocol as agreed by the Sponsor and, by the regulatory authority(ies) (as appropriate), and which was given favourable opinion by the Ethics Committee (EC). The PI or delegate must document and explain any deviation from the approved protocol and communicate this to the trial team at UCL.

A list of activated sites may be obtained from the Trial Manager.

2.3 Co-ordinating centre approval and activation

Training will be performed prior to the activation of the Keele University co-ordinating centre and before recruitment of any participants in the North West Coast and the West Midlands region. A log of those attending the training will be kept in the TMF as a record of participants present. The training may occur in person or via Videoconference.

The trial manager or delegate will notify the Keele University co-ordinating centre of activation in writing.

The Keele University co-ordinating centre must conduct the trial in compliance with the protocol as agreed by the Sponsor and, by the regulatory authority(ies) (as appropriate), and which was given favourable opinion by the Ethics Committee (EC). Any deviation from the approved protocol must be documented, explained, and communicated to the trial team at UCL.

3 Selection of Participants

There will be **NO EXCEPTIONS** (waivers) to eligibility requirements at the time of trial entry. Questions about eligibility criteria should be addressed PRIOR to attempting to randomise a participant.

The eligibility criteria for this trial have been carefully considered and are the standards used to ensure that only medically appropriate participants are entered. Participants not meeting the criteria should not be entered into the trial for their safety and to ensure that the trial results can be appropriately used to make future treatment decisions for other people with similar diseases or conditions. It is therefore vital that exceptions are not made to these eligibility criteria.

Participants will be considered eligible for enrolment in this trial if they fulfil all the inclusion criteria and none of the exclusion criteria as defined below.

3.1 Participant Inclusion Criteria

1. Meeting ICD-11 criteria for generalised anxiety disorder using the revised clinical interview schedule (CIS-R)
2. Scoring ≥ 12 on the CIS-R total score
3. Age 18-74 years (upper age limit to ensure the validity of our measures)

4. Currently taking an SSRI, SNRI or mirtazapine (at specified doses; the full list is in the trial guidance document that all investigators at sites have to follow), for a minimum of 8 weeks prior to randomisation and with good adherence as agreed with PI.
5. Treatment with at least one other antidepressant before their current antidepressant

3.2 Participant Exclusion Criteria

1. Currently taking pregabalin or use within the previous 1 month (i.e. wash-out of 1 month required)
2. Taking regular antipsychotics
3. Have bipolar disorder, psychosis, or alcohol misuse
4. Current or recent opiate dependence where there is a risk of pregabalin abuse
5. Current use of opiates with a daily dose of >15 morphine milligram equivalents
6. Creatinine clearance <30ml/min (measured by eGFR is acceptable).
7. Requirement to use home oxygen machines daily for respiratory problems.
8. Experience breathlessness and score ≥3 on the MRC Dyspnoea scale ('Stops for breath after walking about 100 metres or after a few minutes on the level' or 'Too breathless to leave the house or breathless when dressing or undressing')
9. Regular daily use of z drugs >3.75mg zopiclone or >10mg zolpidem
10. Regular daily use of benzodiazepines or regular night-time use >10mg diazepam or equivalent.
11. Currently receiving psychotherapy and within 6 months of starting therapy
12. Pregnancy, planned pregnancy and women who are breastfeeding
13. Unable to complete self-administered scales in English (some scales are not validated in other languages)
14. Taking part in another CTIMP

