	35. Stevens-Johnson syndrome, toxic epidermal necrolysis, cold sweat 36. Ascites, pancreatitis, swollen tongue, dysphagia 37. Pulmonary oedema, throat tightness 38. QT prolongation, sinus tachycardia, sinus arrhythmia 39. Vision loss, keratitis, oscillopsia, altered visual depth perception, mydriasis, strabismus, visual brightness 40. Convulsions, parosmia, hypokinesia, dysgraphia, Parkinsonism 41. Disinhibition 42. Angioedema, allergic reaction		
	43. Hepatic failure, hepatitis	Very rare (<1/10,000)	The participant will be told to stop the medication and consult their general practitioner for further management.
	44. Respiratory depression	Not known cannot be estimated from the available data)	The participant will be told to stop the medication and consult their general practitioner for further management. For participants who experience breathlessness and score 2 on the MRC Dyspnoea scale, the PI will review and consider reducing the dose. If they reach score 3 or 4 then they will discontinue

2 Selection of Sites/Investigators

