3.5 Screening Procedures and Informed Consent

Patients will be provided with a Participant Information Sheet (PIS) and given sufficient time to read it fully (a minimum of 24 hours). Following a discussion with a medically qualified investigator or suitable trained and authorised delegate, any questions will be satisfactorily answered and if the participant is willing and has the capacity to consent and wishes to participate, informed consent will be obtained. This could be a paper consent form or e-consent and will be signed by a delegated member of site staff.

The local PI or clinical delegate will also review participants who have any cautions for pregabalin, for example renal impairment, co-existing chronic obstructive airways disease, and co-prescription of opioids, benzodiazepines, or z-drugs, and then decide if participants should be randomised. This will be done, when necessary, in consultation with the participant's GP.

If a patient has capacity and is willing to provide verbal consent, but is physically unable to sign the consent form, a witness independent of the trial team will be identified and asked to sign the witness signature field in the consent form, to attest to the patient's verbal consent to participate.

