If a participant experiences intolerable side effects, the dosage may be decreased to the previous dose level at any time during the double-blind period and will be documented. The GP will be informed of any dose changes.

In cases where participants have missed doses, these should be reviewed and discussed by the investigator at the research site to advise on the best dosing plan to remain on trial medication. Participants who discontinue study medication will be invited to all follow up assessments. Once participants have discontinued study medication, they will not be able to re-commence.

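### Exclusion 1 limits earlier pregabalin use only by a 1-month wash-out, so people with a past serious reaction to pregabalin, or in whom it failed, meet every listed entry criterion

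*Protocol*

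**What the plan says.** Exclusion 1 in section 3.2, repeated in the synopsis, reads "Currently taking pregabalin or use within the previous 1 month (i.e. wash-out of 1 month required"). The other 13 exclusions and the 5 inclusions in section 3.1 say nothing about why pregabalin was stopped in the past.

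The opening of section 3 makes the list decisive: "Participants will be considered eligible for enrolment in this trial if they fulfil all the inclusion criteria and none of the exclusion criteria as defined" there. It allows no waivers: "It is therefore vital that exceptions are not made to these eligibility criteria".

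Table 1 in section 1.4 names hypersensitivity among the uncommon risks of pregabalin. Among the rare risks it names Stevens-Johnson syndrome and "Angioedema, allergic reaction". For the rare group, the stated management is that the participant stops the drug and sees the GP.

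Section 3.5 adds a clinical check before randomisation: "The local PI or clinical delegate will also review participants who have any cautions for pregabalin, for example renal impairment". Its other examples are obstructive airways disease and co-prescription of opioids, benzodiazepines or z-drugs. The reviewer then decides whether the person is randomised, consulting the GP where needed.

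**The concern.** The wash-out clause itself expects former users to enter. They are a realistic group: section 1.4 describes pregabalin as licensed for generalised anxiety disorder and commonly used, and the glossary adds epilepsy and pain. Someone who stopped it five weeks earlier because of angioedema, or because it did nothing, satisfies every written criterion.

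Two things are at stake, and they carry different weight.

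- **Safety.** Re-exposing a person with a known serious reaction is avoidable harm. The entry criteria do not carry over a risk that the protocol's own table recognises.
- **Interpretation.** The analysis covers all randomised participants under a treatment-policy approach (sections 8.3.1 and 8.3.6). Earlier non-responders would therefore stay in the primary comparison and could pull the difference towards zero. The protocol does not say whether their inclusion is intended.

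**Working it through.** **1. Does any criterion cover the case?** Take a person who stopped pregabalin more than one month ago after a serious reaction, or for lack of benefit, and who otherwise qualifies.

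- Inclusions 1 to 5 cover diagnosis, CIS-R score, age, current antidepressant and an earlier antidepressant. All are met.
- Exclusion 1 is not triggered, because the wash-out is complete.
- Exclusions 2 to 14 cover other drugs, other conditions, renal and respiratory limits, psychotherapy, pregnancy, language and other trials. None refers to the response to pregabalin.

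The person is eligible as the list is written.

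**2. Does section 3.5 close the gap?** Each example given there is also backed by a listed limit in section 3.2:

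| Example in 3.5 | Listed exclusion in 3.2 |
|---|---|
| Renal impairment | Item 6 (creatinine clearance) |
| Airways disease | Items 7 and 8 (home oxygen, dyspnoea score) |
| Opioids, z-drugs, benzodiazepines | Items 5, 9 and 10 |
| Past reaction to pregabalin (not named) | None |
| Past failure on pregabalin (not named) | None |

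For the risks it names, the protocol does not rely on the review alone. For a past reaction it does. Past failure is not obviously a caution at all.

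**3. Reproducing the sample size.** Inputs from section 8.1: difference 1.6 points, SD 5.6 (the lower of the two given), correlation 0.47, 90% power, 5% significance (two-sided assumed), 20% attrition.

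- Effective SD = 5.6 × √(1 − 0.47²) = 4.94, stated as 4.9.
- n per group = 2 × (1.960 + 1.282)² × 4.9² / 1.6² ≈ 197.1, so 198 by the normal approximation. The protocol states 199.
- 199 / 0.80 = 248.75, so 249 per group and 498 in total, as stated.

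The stated size reproduces, and nothing here is a numerical error.

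**4. Illustrating dilution.** Let f be the share of participants in whom pregabalin has no effect. The expected difference is 1.6 × (1 − f), and power = Φ(difference / (4.9 × √(2/n)) − 1.96). The standard error is 0.491 with n = 199 and 0.439 with n = 249.

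| f (assumed) | Difference | Power, 199 per group | Power, 249 per group |
|---|---|---|---|
| 0% | 1.60 | 90.3% | 95.4% |
| 2% | 1.57 | 89.1% | 94.6% |
| 5% | 1.52 | 87.2% | 93.3% |
| 10% | 1.44 | 83.4% | 90.6% |

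The documents give no value for f. Zero effect in every such person is the worst case short of harm. The figures stay on the points scale used in section 8.1, although the primary analysis is on the log scale.

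**The case against.** The strongest reply is that section 3.5 already deals with safety. It covers any caution, its examples are only examples, and a clinician decides. Section 3.3 also supplements the eligibility check with medical notes. A known pregabalin allergy falls within that review on a natural reading. This largely stands. A reader might infer from the no-waiver rule that a person with a known allergy must be randomised. The documents do not support that: the rule forbids admitting people who fail a criterion and does not oblige anyone to randomise all who pass. What remains is that the safeguard depends on someone raising an item that no criterion names, when some of the criteria are first checked by a research assistant by phone (section 3.3).

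The affected group is also likely to be small. Table 1 puts angioedema and allergic reaction in the rare band and hypersensitivity in the uncommon band, and a person must have both taken pregabalin and reacted to it. This stands too, and it limits the size of the point.

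A reader might see a contradiction with section 4.2.4: "Once participants have discontinued study medication, they will not be able to re-commence". That rule governs study medication after entry. It says nothing about use before the trial, so it does not conflict with exclusion 1.

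Finally, a pragmatic trial may choose to admit earlier non-responders, whose earlier dose, duration or indication may have differed. That is a legitimate choice. The objection is only that the protocol does not show it was made.

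**Conclusion.** The entry criteria leave out past serious reactions to pregabalin, although Table 1 lists such reactions as risks and the discretionary review does not name them. That conclusion rests on the text alone and needs no prevalence assumption. The criteria are also silent on past failure, so such people are admitted by default.

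It would go too far to conclude that the trial is underpowered. The dilution figures depend on an assumed share and an assumed zero effect. At 10%, power is about 83% in the full-attrition case and about 91% if everyone is followed, and section 8.1 expects substantially better follow-up than its 20% allowance.

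Two further inferences are not supported. One is that former users would recognise the drug and break the blind: the documents give nothing to size this, and a criterion based on reaction or failure would still admit former users who stopped for other reasons. The other is that all previously intolerant people should be excluded. Objective 2 is to study adverse effects, and section 4.2.4 uses slow titration and flexible dosing to improve tolerability, so a blanket exclusion would select a more tolerant sample.

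**What to change.** Reconcile section 3.2 and the synopsis with Table 1 and section 3.5:

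1. Add an explicit entry criterion for known hypersensitivity or previous serious adverse reaction to pregabalin. The exact clinical wording is for the sponsor. Check it against the treatment history taken at baseline (section 5.2) and the GP notes (section 3.3).
2. Have the sponsor decide, and state, whether people in whom pregabalin was previously stopped for lack of benefit are eligible. If they are, say that their inclusion is intended.

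The cost is a line or two in the criteria, one question on the screening form and a slightly smaller eligible pool. The sample size need not change on this account.

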3.2.1 Women of Childbearing Potential

A woman is considered of childbearing potential (WOCBP), i.e. fertile, following menarche and until becoming post-menopausal unless permanently sterile. Permanent sterilisation methods include hysterectomy, bilateral salpingectomy and bilateral oophorectomy. A postmenopausal state is defined as no menses for 12 months without an alternative medical cause. However, in the absence of 12 months of amenorrhea, a single FSH measurement is insufficient.

Pregabalin use in the first trimester of pregnancy may cause major birth defects in the unborn child. Pregabalin may cross the human placenta. Pregabalin is excreted into human milk however the effect of pregabalin on infants is unknown. Therefore, female participants of childbearing potential must not become pregnant and must agree to use a highly effective contraception whilst taking the IMP and for 30 days after stopping trial treatment. A highly effective method of birth control is defined as a contraceptive method that can achieve a failure rate of <1% per year when used consistently and correctly. Birth control measures should continue for the duration of trial treatment and can stop 30 days after the last IMP was taken.

Discussions of contraception and chosen method(s) of contraception should be clearly documented in the participants medical notes during the screening visit and prior to randomisation.

All women of childbearing potential will agree to undergo a urine pregnancy test at baseline, and again at the end of the tapering period. Participants will be provided with urine pregnancy test kits and instructions. Participants will also be provided with an additional pregnancy test

kit if any delayed or missed menses occur. A member of the research team at site will call the participant to verbally obtain the results of the pregnancy test. A picture of the results of this pregnancy test should be also provided to the research team at site. The result will be documented on the Case Report Form (CRF).

3.2.2 Birth Control Methods considered as Highly effective

Highly effective contraceptive methods include:

- Combined (oestrogen and progestogen containing) hormonal contraception associated with inhibition of ovulation:
 - Oral
 - intravaginal
 - transdermal
- Progestogen-only hormonal contraception associated with inhibition of ovulation:
 - Oral
 - injectable
 - Implantable (*low user dependency*)
- Intrauterine device (IUD) – (*low user dependency*)
- Intrauterine hormone-releasing system (IUS) – (*low user dependency*)
- Bilateral tubal occlusion – (*low user dependency*)
- Vasectomised male partner – (*low user dependency*). This is a highly effective birth control method provided that the partner is the sole sexual partner of the WOCBP participant and that the vasectomised partner has received medical assessment of the surgical success. Investigators at sites must document azoospermia prior to the female participants' entry into the trial.
- Sexual abstinence, defined as refraining from heterosexual intercourse (i.e., with male partner) when this is in line with the preferred and usual lifestyle of the participant, during the entire period of administering the trial treatment.

(Taken from Clinical Trials Facilitation and Coordination Group, Recommendations related to contraception and pregnancy testing in clinical trials, v1.1, published on 21Sep2020

https://www.hma.eu/fileadmin/dateien/Human_Medicines/01-About_HMA/Working_Groups/CTFG/2014_09_HMA_CTFG_Contraception.pdf?fbclid=IwAR3AY5Ha0ESDyqlBeUaYI9VTFWmx9bbt8NZ-80N-5ME6pkBb1UHvFsTwqlQ

3.2.3 Male Participants

A man is considered fertile after puberty unless permanently sterile by bilateral orchidectomy. In clinical practice, fertile male patients with partners who are women of childbearing potential are not required to use precautions to prevent pregnancy whilst taking pregabalin. Therefore, male participants will not be required to take precautions to prevent pregnancy whilst participating in the trial.

3.3 Recruitment

General practices, who have agreed to take part, across 4 geographical areas: London, Bristol, North West Coast and West Midlands, will carry out record searches to identify people who have been prescribed an antidepressant for at least 8 weeks and will contact potential participants with the participant information sheet and ask those interested to contact the

research team by all possible means, including a weblink. The initial contact will be via post, although GP practices may also text patients with a reminder to respond to the invitation letter. GPs and other primary care clinicians will also be invited to refer directly to the study team with patient agreement. A trained research assistant will then establish by phone some of the eligibility and exclusion criteria and screen with a GAD7 questionnaire to assess anxiety symptoms. This GAD7 screen will not be part of the eligibility criteria but is designed to increase the likelihood that participants will meet our eligibility criteria when they are assessed at the baseline visit. It is designed to improve the efficiency of the fieldwork. The consent will be obtained for the assessment of eligibility, supplemented by details from medical notes such as concerning renal impairment. For those potentially eligible for the trial, a baseline assessment will be performed online, or face to face in a general practice or at home or at University premises to establish eligibility.

We recognise that general practice is under considerable pressure at present, and we have designed this study to have minimal impact on the practice. For example, UCL and University of Bristol will be the Investigator sites (with Keele University acting as a co-ordinating centre for UCL participants recruited in the West Midlands region) and the practices will be research sites with no PI oversight required, this will minimise the paperwork for the practice.

We plan a 6-month internal pilot to estimate our recruitment rate and test the robustness of our procedures. The internal pilot will occur at the UCL site only so we can adapt and finalise any procedures before opening the University of Bristol site and activating the Keele University co-ordinating centre for UCL participants recruited from the West Midlands and North West Coast. Table 2 shows the internal pilot progression criteria.

Table 2. Internal pilot progression criteria

Progression criteria	Red	Amber	Green
Trial recruitment % complete	50%	70%	100%
Recruitment rate/region /month	4 randomisations per month	6	8
Number of GP practices opened	8	11	16
Total number of participants recruited	24	36	48

In addition to the recruitment targets given above, we will set a target of 90% for participants starting study medication, 80% for completing follow up assessments at the primary endpoint and as a measure of acceptability, we will require 70% of the participants to be taking study medication at the primary outcome assessment at 12 weeks. This will be reviewed at the end of the pilot and results presented to the Trial Steering Committee and Data Monitoring Committee.

